# 1.2. Study Design

[figure not shown]
Study FVAA is a Phase 2, randomized, double-blind, placebo-controlled study to evaluate the efficacy and safety of LY3972406 in adults with moderate-to-severe plaque psoriasis.

The study duration will be approximately 29 weeks over 3 study periods:

- **Screening**: occurs within 35 days before the planned randomization visit (baseline; Visit 2, Week 0)
- **Double-blind treatment period**: lasts for 12 weeks from baseline
- **Posttreatment follow-up**: lasts for up to 12 weeks after last treatment visit (or last dose for early discontinuation)

The study design is illustrated in Figure FVAA.1.1. The study will have 2 stages:

- In Stage 1, participants will be randomly assigned to receive LY3972406 CCl or placebo.
- Stage 2 may be initiated at the sponsor's discretion after review of the interim analysis data from Stage 1 to collect additional safety and efficacy data at the CCI dose level. If Stage 2 is implemented, the participants will be randomly assigned to receive either
  - LY3972406 CCI
     LY3972406 CCI
     or placebo,
     OR
  - o LY3972406 CCl or placebo.

Abbreviations: ED = early discontinuation; n = number of participants; CCI V = Visit; W = Week.

- a Visits 803 and 804 are not required for all participants.
- b For the follow-up visits, the weeks in parentheses indicate weeks after the last dose.

Figure FVAA.1.1. Illustration of study design for clinical protocol J4H-MC-FVAA.

# 2. Statistical Hypotheses

The primary objective is to demonstrate that LY3972406 is superior to placebo in achieving PASI 75 at Week 12. Thus, the null hypothesis to be tested in relation to the primary estimand is as follows: LY3972406 is not different from placebo in achieving PASI 75 at Week 12.

# 2.1. Multiplicity Adjustment

Adjustment for multiple comparisons will not be employed in the analysis for this study.

# 3. Analysis Sets

For purposes of analysis, the following populations are defined:

Population	Description
Screening	All patients who signed informed consent.
Modified intent-to-treat (mITT)	All participants randomly assigned to study
	intervention and who take at least 1 dose of study
	intervention. Participants will be analyzed
	according to the study intervention to which they
	were assigned.
Per-protocol	All randomized participants who do not commit an
	important protocol deviation that could potentially
	compromise efficacy results.
	Participants will be analyzed according to the
	study intervention to which they were assigned.
Safety	All randomized participants who received at least
	1 dose of study intervention.
	Participants will be analyzed according to the
	study intervention they received.
Pharmacokinetic (PK)	All participants randomly assigned to study
	intervention and who take at least 1 dose of study
	intervention and have PK data available.
Follow-up	All mITT participants who have entered the
	posttreatment follow-up period.
	Participants will be analyzed according to the
	study intervention to which they were assigned.

**Note:** In the context of this table and throughout the protocol, the terms "study intervention" and "treatment" may be used interchangeably.

# 4. Statistical Analyses

#### 4.1. General Considerations

Statistical analysis of this study will be the responsibility of the sponsor or its designee.

This study has 2 stages. If Stage 2 is initiated, all data from Stage 1 will be combined with Stage 2 data for the primary outcome analysis. If Stage 2 is not initiated, the primary outcome analysis will occur at the end of Stage 1. The primary outcome lock will occur once all subjects have completed the double-blind period or discontinued study intervention and 100% of the primary endpoint data is available.

Primary and secondary hypotheses will be tested at a 1-sided 0.025 nominal level unless otherwise specified.

Unless otherwise specified, the modified intent-to-treat population will be used for all efficacy analyses.

ICEs will be summarized by the number of occurrences for each study intervention during the double-blind treatment period (through Visit 9).

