## Data analysis methods

Treatment comparisons of categorical efficacy, patient-reported outcomes, and quality-of-life variables will be made using a Cochran-Mantel-Haenszel test stratified by prior exposure to biologic therapy for psoriasis (biologic naïve versus experienced). The 95% confidence intervals associated with the treatment response rate and treatment difference will be reported.

Treatment comparisons of continuous efficacy, patient-reported outcomes, and quality-of-life variables will be made using the mixed model for repeated measures (MMRM). The model will include the following as fixed factors: treatment, baseline value, visit, prior exposure to biologic therapy for psoriasis (biologic naïve versus experienced), and the interaction of treatment-by-visit. Type III sums of squares for the least squares means will be used for the statistical comparison; the 95% confidence interval will also be reported. The covariance structure to model the within-participant errors will be unstructured. If the unstructured covariance matrix results in a lack of convergence, the heterogeneous Toeplitz covariance structure, followed by the heterogeneous autoregressive covariance structure, will be used. In the event that none of the MMRM models converge, an analysis of covariance will be used with treatment, baseline value, and prior exposure to biologic therapy as fixed factors.

Fisher's exact test will be used for categorical safety data including AE, baseline, and discontinuations. Continuous vital sign, electrocardiogram (ECG), and laboratory values will be analyzed by analysis of covariance with treatment and baseline value in the model.

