# 4.3. Primary Estimand Analysis

Treatment comparisons between each LY3972406 dose and placebo in the proportion of participants achieving PASI 75 at Week 12 will be analyzed using the Cochran-Mantel-Haenszel

test stratified by prior exposure to biologic therapy for psoriasis (biologic naïve versus experienced) with NRI, as described. Participants who fail to complete the 12-week treatment period due to an ICE related to study intervention or violate the concomitant medications rules will be treated as nonresponders. The 95% confidence intervals associated with the treatment response rate and treatment difference to placebo will be provided by treatment. The primary analysis will be conducted on the modified intent-to-treat analysis set when all participants reach Week 12 or have discontinued during the treatment period.

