## 4.4. Secondary Estimands Analysis

Proportions of participants achieving the following scores will be analyzed using the Cochran-Mantel-Haenszel test stratified by prior exposure to biologic therapy for psoriasis (biologic naïve versus experienced) with NRI:

- PASI 90
- PASI 100
- sPGA 0 (clear)
- sPGA 0 or 1 (clear or almost clear)
- PSSI 0

Participants who fail to complete the 12-week treatment period due to an ICE related to study intervention or use prohibited concomitant medications will be treated as nonresponders. The 95% confidence intervals associated with the treatment response rate and treatment difference will be provided by treatment.

Treatment comparisons between each LY3972406 dose and placebo in the PASI percent change, body surface area mean change from baseline, PSSI mean change from baseline to Week 12, and patient reported outcomes will be analyzed using the MMRM model, as described in Section 4.1. No missing data imputation will be performed. The least squares mean and 95% confidence interval will be summarized by treatment.

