## 4.8.2. Subgroup Analyses

Subgroup analyses of the primary endpoint and secondary endpoints will be made to assess consistency of the intervention effect across the following subgroups:

- age group: younger than 65 versus 65 years or older
- sex: female versus male
- ethnicity: Hispanic or Latino versus Non-Hispanic or Latino
- race: White versus Black versus Other
- prior exposure to biologic therapy: biologic naïve versus biologic experienced, and
- body mass index: less than 30 versus 30 or greater.

If the number of participants is too small (less than 10%) within a subgroup, then the subgroup categories may be redefined prior to unblinding the study.

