# 4.9. Interim Analyses

Analyses for the primary database lock will be conducted as described in Section 9.3 of the protocol. If Stage 2 is not initiated, the primary outcome database lock will occur when all the participants from Stage 1 have completed the Week 12 visit or have discontinued the study intervention. If Stage 2 is initiated, the primary outcome database lock will occur when all the participants from Stage 2 have completed the Week 12 visit or have discontinued the study intervention.

Two interim analyses may be conducted during Stage 1 prior to the primary database lock at the sponsor's discretion. One interim may occur when approximately 50% to 90% of participants from Stage 1 have completed the Week 12 visit or have discontinued the study intervention. Another interim analysis may be conducted when approximately 90% to 100% of participants from Stage 1 have completed the Week 12 visit or have discontinued the study intervention. The results of either interim analysis can be used by the sponsor's internal assessment committee (IAC) to recommend if Stage 2 should be initiated.

The interim analyses may include safety, PK, PD, and efficacy data. The data may be used for internal decision making, development of PK and PD modeling, or both. An assessment of unblinded interim data will be conducted by an IAC with a limited number of individuals who do not have direct site contact or data entry or validation responsibilities. Study sites will receive information about interim results only if they need to know for the safety of their participants.

The study will not be stopped early due to efficacy.

Unblinding details are specified in the blinding unblinding document.

At the discretion of the sponsor, prespecified interim analyses may not be conducted.

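### A regimen opened only in Stage 2 would be tested against placebo from both stages, with no stage term and no concurrent-placebo check visible

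*SAP*

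**What the plan says.** - **Pooling.** SAP 4.1: "If Stage 2 is initiated, all data from Stage 1 will be combined with Stage 2 data for the primary outcome analysis".
- **Binary endpoints.** The primary CMH analysis (SAP 4.3) is a "test stratified by prior exposure to biologic therapy for psoriasis", and SAP 4.4 repeats this for the secondary responders: "Mantel-Haenszel test stratified by prior exposure to biologic therapy for psoriasis". Prior biologic exposure is the only stratum.
- **Continuous endpoints.** SAP 4.1, Data analysis methods: "The model will include the following as fixed factors: treatment, baseline value, visit, prior exposure to biologic therapy for psoriasis", plus treatment-by-visit. If no MMRM converges, "an analysis of covariance will be used with treatment, baseline value, and prior exposure to biologic therapy as fixed factors". Neither model contains stage.
- **Comparator.** SAP 4.1 compares each dose with placebo and does not qualify placebo by stage. The mITT set in SAP 3 takes every randomised and dosed participant, and no concurrent-control set is defined.
- **Stage 2.** SAP 1.2: "Stage 2 may be initiated at the sponsor's discretion after review of the interim analysis data from Stage 1". Under SAP 4.9 an internal committee uses unblinded interim results "to recommend if Stage 2 should be initiated". In the visible text Stage 1 has one LY3972406 regimen plus placebo, while one of the two Stage 2 options has two regimens plus placebo (Protocol 4.1, SAP 1.2). SAP 5 likewise allows for Stage 2 with or without an extra arm.
- **Consistency checks.** SAP 4.8.2 begins: "Subgroup analyses of the primary endpoint and secondary endpoints will be made to assess consistency of the intervention effect across the following subgroups". Stage is not in the list that follows.

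**The concern.** If the two-regimen option opens, at least one regimen will have been randomised only in Stage 2. Its pooled control group then contains Stage 1 placebo patients, who were enrolled earlier and could not have been assigned to it. Any change in placebo PASI 75 response between stages passes into that dose's estimated effect, and no term in the model absorbs it.

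The latest protocol amendment widened eligibility to women of childbearing potential and made biopsy optional. The documents do not say where this falls relative to the stages, so it shows a possible route for drift, not evidence of it.

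At stake is the reading of one dose's result in a study meant to guide development, tested at a one-sided nominal 0.025. Nothing arises if Stage 2 stays closed, and the non-concurrent part also needs the extra arm.

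**Working it through.** **Inputs.** From the documents: one-sided 0.025 (SAP 4.1) and about 35 further participants in Stage 2 (Protocol 2.3.3). Stage 1 size, allocation ratios, placebo rate, target difference and power are redacted, so there is no stated figure to reproduce. Assumed instead: 15, 20, 30 or 40 Stage 1 placebo patients; Stage 2 placebo/new dose of 12/12, 11/12, 7/14, 17/18 or 12/23 (20 layouts in all); a Stage 1 placebo rate of 5%; a Stage 2 rate of 5%, 7%, 10% or 15%.

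**1. Drift bias for a Stage-2-only dose.**
Bias = w × (p2 − p1), where w = Stage 1 placebo / all placebo.
For 30 and 12: w = 30/42 = 0.714. A move from 5% to 10% gives 0.714 × 5 = +3.6 points. A 5-point fall gives −3.6 points, against the drug. Over the 20 layouts w runs from 15/32 = 0.47 to 40/47 = 0.85.

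**2. Null error for that dose.** Exact binomial enumeration, rejecting when z > 1.96, with
z = (x − n·m/N) / √[n·(N−n)·m·(N−m) / (N²(N−1))],
where x = responders on the dose, n = its size, m = all responders and N = all patients compared. Biologic strata are collapsed and the dose is given the Stage 2 placebo rate.

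| Stage 1 placebo / Stage 2 placebo / new dose | w | No drift (5%) | 5% to 7% | 5% to 10% | 5% to 15% |
|---|---|---|---|---|---|
| 15/17/18 | 0.47 | 0.015 | 0.029 | 0.050 | 0.083 |
| 15/12/12 | 0.56 | 0.037 | 0.057 | 0.084 | 0.118 |
| 30/12/12 | 0.71 | 0.025 | 0.044 | 0.078 | 0.144 |
| 30/17/18 | 0.64 | 0.037 | 0.056 | 0.086 | 0.139 |
| 40/12/23 | 0.77 | 0.050 | 0.084 | 0.138 | 0.233 |
| Range, 20 layouts | 0.47–0.85 | 0.007–0.067 | 0.016–0.092 | 0.033–0.138 | 0.069–0.233 |

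The no-drift column already spans 0.007 to 0.067 because the test is discrete in small samples. Drift should therefore be read along a row, not from the spread between layouts. Against concurrent placebo only, the error never exceeds 0.026.

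**3. Power given up by concurrent placebo alone (10% vs 50%).** For 30/12/12, 86% pooled falls to 60%. Over the 20 layouts the ranges are 77–97% pooled and 46–79% concurrent.

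**4. A dose randomised in both stages.** Bias = (Stage 2 share of the dose arm − Stage 2 share of placebo) × drift. With 30:30 then 12:12 the shares are equal and the bias is zero. With 30:30 then 14:7 (dose:placebo) it is (14/44 − 7/37) × 5 = (0.318 − 0.189) × 5 = 0.6 points.

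**5. Opening Stage 2 on Stage 1 results.** Assumed rule: open if the observed Stage 1 difference is at least 10 or 20 points. True rates are 10% vs 30% or 40%, with no drift, 15–40 per arm in Stage 1 and 12:12 in Stage 2. For the dose used in both stages, exact bias is +0.2 to +5.2 points in the pooled estimate given opening, −8 to −28 points in the Stage 1 estimate given not opening, and −0.1 to −2.5 points averaged over both. With 5% or 10% in both arms, overall one-sided error is 0.004–0.029.

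**The case against.** **The comparator is not undefined.** A reader might infer that the plan leaves open which placebo patients a Stage-2-only dose is compared with. It does not. All data are combined, the mITT set is all randomised and dosed participants, and each dose is compared with placebo. Together these give all placebo from both stages. What remains is that the choice is not spelled out for such a dose, and its no-drift assumption is neither named nor checked. This objection stands and sets the scope of the point.

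**Pooling is a defensible choice.** It has much more power. In the assumed grid the pooled placebo rate also has lower root mean square error in all 20 layouts for rises from 5% to 7%, 10% or 15% (30/12/12, 5% to 15%: 8.2 vs 10.3 points). The reverse holds for a fall from 15% to 5% (8.7 vs 6.3 points). This too stands: the case is for stating and checking the assumption, not for abandoning pooling.

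**Selection.** A reader might infer that opening Stage 2 on good Stage 1 data inflates false positives. The calculation does not support that. The upward bias given opening is matched by a downward one given not opening, the average is slightly against the drug, and the null error stays near or below nominal.

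**A check may exist out of sight.** The exploratory list is missing from the public SAP, Protocol 9.4 allows further interim analyses in a separate document, and a discretionary interim at 90–100% of Stage 1 may include efficacy. An unseen by-stage analysis cannot be excluded. None of the visible text prespecifies one for the final pooled data.

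**Conclusion.** The point holds as a low-cost improvement. As written, a regimen randomised only in Stage 2 is tested partly against placebo patients who could not have received it. The validity of that comparison rests on an unstated assumption of no between-stage drift, with no check visible in the public text.

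The size depends on redacted arm sizes and on drift that is assumed, not observed. In the 30/12/12 example, a 5-point rise from 5% adds about 3.6 points of bias and takes one-sided null error from 0.025 to 0.078; a fall works against the drug. A dose used in both stages is exposed to drift only if allocation changes between stages, and then by under a point for a 5-point drift when 1:1 becomes about 2:1. The selection effect of opening Stage 2 is a reason to show Stage 2 alone, not evidence of inflated error.

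**What to change.** Before first unblinding, amend SAP 4.1, 4.3 and 4.4:

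1. **Dose randomised in both stages.** Add stage to the CMH strata, stage and stage-by-visit to the MMRM, and stage to the ANCOVA fallback.
2. **Dose randomised only in Stage 2.** If all placebo is the intended comparator, say so and label the result as relying on no between-stage drift. Prespecify a concurrent-placebo sensitivity analysis restricted to Stage 2 data. For continuous endpoints a stage main effect is not a substitute: in a one-visit arm-plus-stage model, the new dose's contrast still put weight 0.27–0.54 on Stage 1 placebo, offset through the shared dose.
3. **Reporting.** Tabulate response by arm and stage, including Stage 2 alone for the dose used in both stages, since that estimate is free of the decision to open Stage 2.

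Which comparator is primary stays the sponsor's choice, given the power loss shown above.

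**Cost.** No new data. With biologic strata kept (15–40% experienced assumed, 10% vs 40%), the stage stratum costs about 0.4 points of power (30:30 then 12:12) to 1.6 points (20:20 then 14:7). Stage 2 cells by biologic history will be sparse, and a few stage-restricted runs are added.

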## Changes to the data analysis methods

Any change to the data analysis methods described in the protocol will require an amendment ONLY if it changes a principal feature of the protocol. Any other change to the data analysis methods described in the protocol, and the justification for making the change, will be described in the clinical study report. Additional exploratory analyses of the data will be conducted as deemed appropriate.

#### Continuous and categorical data analyses

Continuous data will be summarized in terms of the mean, standard deviation, minimum, maximum, median, and number of observations. Categorical data will be summarized as frequency counts and percentages. Comparisons between each LY3972406 dose and placebo will be performed for all analyses in the treatment period with no adjustment for multiple comparisons.

#### **Baseline definitions**

For the treatment period efficacy, health outcomes, quality-of-life, and safety analyses, baseline is defined as the last available value before the first drug administration, which in most cases will be the measure recorded at Week 0 (Visit 2). Change from baseline will be calculated as the visit value of interest minus the baseline value. For safety analyses using a baseline period, the baseline period is defined as the time from Visit 1 up through the date and time of the first dosing at Visit 2. Percent change from baseline will be calculated as  $100 \times (visit \ value - baseline \ value)$  / baseline value.

## Data analysis methods

Treatment comparisons of categorical efficacy, patient-reported outcomes, and quality-of-life variables will be made using a Cochran-Mantel-Haenszel test stratified by prior exposure to biologic therapy for psoriasis (biologic naïve versus experienced). The 95% confidence intervals associated with the treatment response rate and treatment difference will be reported.

Treatment comparisons of continuous efficacy, patient-reported outcomes, and quality-of-life variables will be made using the mixed model for repeated measures (MMRM). The model will include the following as fixed factors: treatment, baseline value, visit, prior exposure to biologic therapy for psoriasis (biologic naïve versus experienced), and the interaction of treatment-by-visit. Type III sums of squares for the least squares means will be used for the statistical comparison; the 95% confidence interval will also be reported. The covariance structure to model the within-participant errors will be unstructured. If the unstructured covariance matrix results in a lack of convergence, the heterogeneous Toeplitz covariance structure, followed by the heterogeneous autoregressive covariance structure, will be used. In the event that none of the MMRM models converge, an analysis of covariance will be used with treatment, baseline value, and prior exposure to biologic therapy as fixed factors.

Fisher's exact test will be used for categorical safety data including AE, baseline, and discontinuations. Continuous vital sign, electrocardiogram (ECG), and laboratory values will be analyzed by analysis of covariance with treatment and baseline value in the model.

#### Handling of missing, unused, and spurious data

Handling of missing, unused, and spurious data is addressed prospectively in the overall statistical methods described in the protocol and in this document, where appropriate. Adjustments to the planned analyses are described in the final clinical study report.

Missing data imputation is not to be confused with estimand strategy. Missing data of categorical efficacy, patient-reported outcomes, and quality-of-life variables will be imputed using a nonresponder imputation (NRI) method, and the missing data will be considered as nonresponder. For continuous variables, missing data will not be imputed.

When NRI is applied, participants with missing data will be considered as nonresponders regardless of whether they have at least 1 postbaseline data.

# 4.2. Participant Dispositions

A detailed description of participant disposition will be provided, including a summary of the number and percentage of participants entered into the study and randomized; the number and percentage of participants who complete the study or discontinue, both overall and by reason for discontinuation; and the frequency and percentage of patients who discontinued study treatment. A summary of important protocol deviations will be provided.

